Pending incarceration in the next 30 days Homicidal or otherwise behaviorally disturbed requiring immediate attention. High Risk for suicide as determined by answering 'yes' to questions 4 and/or 5 on C-SSRS at screening Blood pressure <90 mm Hg (systolic) or <60 mm Hg (diastolic). If this value is out of normal range, the investigator and a study clinician will decide subject inclusion or exclusion on a case-by- case basis Heart rate and/or pulse<50 bpm at screening-sitting An Estimated Glomerular Filtration Rate eGFR<90 mL/min/1.73m² A history of, or current seizure disorder (excluding childhood febrile seizures) Inability to read and/or understand English. For example, does not understand the informed consent as demonstrated by failing to answer 9/10 questions correctly on the guiz Pregnant or breastfeeding Currently taking sympathomimetic drugs, or a thiazolidinedione antidiabetic An ALT and/or AST that is at > 4X the top limit of normal A Child-Pugh score >7 Currently receiving opioids for pain management In a treatment study where medication was administered in the last 30 days. Currently using medications that are known to be strong or moderate inhibitors of CYP2D6 such as fluoxetine, paroxetine, mirabegron, bupropion, quinidine, terbinafine, cimetidine, cinacalcet, duloxetine, or fluvoxamine In a methadone maintenance or buprenorphine treatment program within the last 30 days Pregabalin (PGB) or PGB-PLA given orally at a *starting* dose of up to 400 mg on day 1, up to 600 mg daily on Day 2 through Day 4, tapered to 100 mg daily Study Product, Dose, by Day 7; Lofexidine (LFX) starts at 1.62 mg on day 1, 2.16 Day 2 through Day Route, Regimen 4, tapering to 0.72 mg by Day 7. After starting dose on Day 1, both study drug doses can be reduced or withheld depending upon patient's clinical observations for Days 1-7. On day 8, subjects are offered an injection of XR-NTX if they provide a urine sample that is negative for opioids, buprenorphine, and fentanyl, and pass a naloxone challenge. All subjects, regardless of whether or not they receive XR-NTX, will be given a list of referrals and help with making an appointment for follow-up treatment when they leave the inpatient detoxification program. The following "comfort" medications are suggested for treatment of withdrawal symptoms that are not suppressed by study medications: ondansetron 4 mg or 8 mg tid PO PRN for nausea and vomiting, trazodone 100 mg HS PRN insomnia, loperamide 2 mg qid PO PRN diarrhea, and a non-steroidal such as **Comfort Medications** Ibuprofen 600 mg qid PO PRN for aches and pains or acetaminophen 650 mg (2 tablets 325 mg) PO gid PO PRN, cyclobenzaprine 5 mg tid PO PRN for muscle aches and pains, and hydroxyzine 25 mg qid PO PRN anxiety. In cases of QTc prolongation that are not >550ms or judged to require stopping study medications, diphenhydramine 50 mg hs PO PRN may be used for insomnia, and trimethobenzamide 300 mg gid PO PRN for nausea.

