Subjects are admitted to the inpatient unit, randomized to one of the two study medication conditions, and will need to demonstrate withdrawal before starting study medications by having a COWS >/= 6 and a SOWS >/= 4. LFX and PGB dosing will begin at 12:00 on day 1 and a study drug taper will be done from days 5-7. Dose times follow the schedule outlined above and adjustments will be made based on BP changes and/or other AEs. Administration of LFX will be withheld or reduced in cases of dizziness or lightheadedness, clinically significant hypotension and/or the BP changes described above. We will explain to participants the importance for adequate oral hydration during the consenting process and throughout the detox. Similar procedures will be applied to PGB in cases of excessive sedation, dizziness, peripheral edema, or other problematic side effects that appear related that medication.

Dosing schedules are in Tables 2 and 3. Assessments for Day 1 through 7 include:

- 1) ECG is obtained before the 12:00 dose of study medications on Day 1 and before the 08:00 dose of study medications on Day 2-7
- 2) VAS is given before the first dose of study medication at 12:00 on Day 1 and before the 16:00 dose on Day 1. On Day 2-7, the VAS is given before the first dose of study medications at 08:00 and before the 16:00 dose of study medications
- 3) ISI given before the 12:00 dose of study medications on Day 1, and before the 08:00 dose of study medications on Days 2-7
- 4) COWS is given around 12:00 on Day 1 before the first dose of study medication; and around16:00 before the next dose of study medication. If subject is admitted without the requisite withdrawal (COWS >/= 6 and SOWS >/= 4), subsequent COWS and SOWS can be administered before the first dose of study medication until dosing criteria is met.
- 5) SOWS-G is given around 12:00 on Day 1 before the first dose of study medication; and around 16:00 before the next dose of study medication
- 6) POSS is given prior to all doses (08:00, 12:00, 16:00 and 20:00) of study medication
- 7) Sitting and standing blood pressure and pulse are taken prior to each dose of study medication and 1 to 2 hours after dosing, (can use manual blood pressure check if considered necessary)
- 8) Weight taken 1x at screen and Day 15 and recorded on the physical form
- 9) Adverse events/SAEs recorded daily
- 10) Concomitant medication records reviewed and recorded each day
- 11) C-SSRS is given at the end of each study day

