10.11 STUDY MEASURES; SEE TABLES 1 FOR SCHEDULES OF ADMINISTRATION

- 1. **Medical History:** Done by the appropriate clinical delegated individual at screening
- 2. Physical/Weight: Done at Screen; and at Day 15
- 3. Pulse and blood pressure: done sitting and standing 1X at screen, done Day 1 through Day 7 done before receiving Study Medication and 1 2 hours after receiving medication, 1X on Day 8, 1X (sitting only) on Day 10 (sitting only), and 1X on Day 15
- 4. ECG: 1X at Screen, 1X each day for Day 1 through Day 7
- 5. Complete Blood Count with diff and PLT: Done at Screening and Day 10
- **6.** Chemistry and calcium: Done at Screening and at Day 10 or Day 15 if not obtained at Day 10
- 7. Magnesium Screening (magnesium need not be repeated at EOS)
- 8. Creatine Kinase at screening and Day 8, and early termination
- 9. Hepatitis B and C done at screening
- 10. Urinalysis with reflex microscopy: Done at Screening and Day 10
- **11. Urine Toxicology Drug Screen.** CLIA Waived and FDA approved on-site test with Buprenorphine, or get an additional buprenorphine test, done at screen, day 8/9, day 10, and day 15.
- **12. Urine Fentanyl**. Done at Screen, Day 1, Day 8/9, Day 10, and Day 15.
- 13. Urine Xylazine . Done at Screen, Day 1, Day 8/9, Day 10, and Day 15.
- 14. Urine pregnancy test: Screen and Day 1, Day 8/9 prior to the XR-NTX injection, and at Day 15
- 15. Adverse Events: Collected by research staff at each visit, Day 1 through Day 15
- **16. Clinical Global Impression Scale (CGI;** Guy,1976): A brief severity rating of overall health at time of interview using a 7-point Likert scale. Completed by a study staff person and the subject. Administered at day 1, day 8, and EOS
- 17. Clinical Opioid Withdrawal Scale (COWS; Wesson & Ling, 2003): An 11-item, staff administered instrument that measures objective signs of opiate withdrawal. Done 1X at screen, 2X daily Day 1 through Day 7, 2X (naloxone challenge) on Day 8* (optional), and 1X on Day 10, and 1X Day 15
- **18. Short Opioid Withdrawal Scale** (SOWS-Gossop; Gossop, 1990): A 10-item, staff administered scale that measures patient's perceptions of opiate withdrawal. Done 1X at screen; 2X daily Days 1 Day 7; and 1X on Days 8,10, and 15.
- **19. CONCOMITANT Medication** (CONMEDS): Any prescribed or non-illicit non-Study Medications used 30 days before screening, and on Day 1 through EOS

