13.0 STATISTICAL PLAN

13.1 DATA ANALYSES

[name], the CSA Statistician, and his staff will perform data analyses. Prior to analyses, standard data screening/cleaning procedures will be applied. These procedures will screen the data for data-entry errors, check for outliers, assess the extent and pattern of missing data, and check that appropriate assumptions of normality are met whenever necessary.

13.2 **SAMPLE SIZE DETERMINATION**

Power Analyses: The primary goal of this study is to determine if the PBG/LFX combination versus LFX/PGB-PLA is safe and effective in OUD individuals, and shows a reduction in opioid–related withdrawal effects greater than lofexidine alone. To assist in this determination, we provide power for the primary comparison of longitudinal subjective withdrawal measures, comparing the groups on rate of decrease across days, using a linear group by time effect for the mixed effects models described above. We have one primary outcome, so use an alpha level of 0.05, and we use two- sided tests. 90 subjects, approximately 30 from each of three sites (MMTC and PENN might have more than 30), who will be randomized into two groups, with 30 assigned to LFX/PGB-PLA, and 60 to LFX plus a starting daily dose of 400 mg of PGB and increasing to 600mg PGB on day 2. Assuming an overall dropout rate of 40%, and within-subjects' correlations of 0.5, the methods of Hedeker et al (Hedeker, Gibbons and Waternaux, 1999) show that this provides 80% power for a group by linear time interaction effect of Cohen's d=0.44 standard deviations between the two groups.

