13.3 STATISTICAL METHODS

13.3.1 Primary Outcome - Reduction in SOWS-Gossop criterion. The primary outcome will be reduction in subjective withdrawal as measured by the SOWS - Gossop (scores range from zero to 30). The groups will be compared on the 14 repeated SOWS-Gossop responses obtained during the seven-day detoxification period, using linear mixed-effects regression models; the SOWS-Gossop total will be regressed on a three-level factor for site, and a two-level factor for medication group, with time and group by time effects. The covariance structure will include a random intercept and correlated residuals, with a random slope included if necessary for fit. Contrasts between the PGB group and the PGB-PLA group will be estimated from the model. Exploratory analyses of heterogeneity of dose effects across sites will be performed including a site by dose interaction term in the main model.

These models will provide valid estimates and tests if any missing data is statistically ignorable (Laird, 1998). Dropout may be associated with reports of subjective withdrawal, and will be ignorable if available subjective scores prior to dropout are predictive of dropout. To assess possible effects of non-ignorability on inference, we will perform sensitivity analyses using pattern- mixture models and selection models. For pattern mixture models, subjects are grouped on the basis of their pattern of missing data. Usually, rarely occurring patterns are grouped, so as to keep the number of pattern-groups at a manageable level. This grouping defines a nominal variable, which is then used as a predictor in the analyses, although a covariate representing missingness on a continuous scale can also be used. The regression coefficients associated with this variable, and its interactions with the other predictors, quantify how response-predictor relationships differ across the different patterns of missingness. Overall predictor effects may be found by averaging over the patterns (Little, 1993). For longitudinal data, subjects are usually stratified according to the visit after which they dropped out. Hedeker and Gibbons (1997), and Hedeker and Rose (2000), apply these methods to mixed effects models in longitudinal data. Selection models (Little, 1995; Kenward, 1998; Verbeke and Molenberghs, 2000) take a different approach, by explicitly modeling the probability of drop out, and incorporating the predicted probabilities

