into the main longitudinal analysis. Heuristically, this can be thought of as a two-stage process, but usually the two steps are performed as part of a single model. Any approach to non-ignorability requires us to make assumptions on the variables associated with missing data, and on the form of the relationship between the variables and dropout. Comparisons between the predictions of the primary analyses, and each set of pattern mixture and selection models, provides some evidence for assessing the sensitivity of results to missing data.

13.3.2 Secondary Outcomes. Completion of and receipt of antagonist treatment: Our completion threshold criterion is based on the study of Fishman et al (2019), where completion of detoxification was defined as "proportion of participants completing the study, defined as having received at least 1 dose of study medication on day 7 and completing the 3.5- hour post dose SOWS-Gossop assessment on day 7. Receipt of antagonist treatment will be defined as completion of the process to receive antagonist treatment and receipt of the first dose.

We will define a three-category ordinal response: (1) failure to complete detoxification, (2) completion with failure to start antagonist treatment, (3) completion and receipt of antagonist treatment. We will compare these groups using ordinal logistic regression models, with a three-level factor for site, and a two-level factor for medication group, as the explanatory variables.

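### The ordinal detoxification/XR-NTX model in 13.3.2 leaves out the pre-dose SOWS-Gossop score; adding it is a cheap gain in precision, not the repair of an invalid test

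*Combined protocol and SAP*

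**What the plan says.** Section 13.3.2 sets up the outcome as follows: "We will define a three-category ordinal response: (1) failure to complete detoxification, (2) completion with failure to start antagonist treatment", the third level being completion with receipt of the antagonist. The model is ordinal logistic regression "with a three-level factor for site, and a two-level factor for medication group, as the explanatory variables". No baseline covariate is named, and no adjusted sensitivity analysis of this outcome is planned.

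Three other places bear on this:

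- **Section 9.1.2** schedules the score before treatment: "SOWS-G is given around 12:00 on Day 1 before the first dose of study medication". COWS and SOWS may be repeated until the dosing threshold (COWS at least 6, SOWS at least 4) is reached.
- **Section 13.3.1**, on missing data in the primary model, says "Dropout may be associated with reports of subjective withdrawal".
- **Section 10.13.3** says that patients often leave because of the discomfort of withdrawal and then do not move to naltrexone.

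Section 13.2 gives the allocation ("with 30 assigned to LFX/PGB-PLA, and 60 to LFX plus a starting daily dose") and the test level ("so use an alpha level of 0.05, and we use two- sided tests"). Its power statement covers the primary outcome only.

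**The concern.** The outcome is decided first by whether the patient stays through detoxification and then by whether XR-NTX is given. The protocol's own account is that subjective withdrawal pushes patients off both steps. A measure of subjective withdrawal taken before any study drug is therefore a natural baseline predictor, and it costs nothing more to collect.

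Two things are at stake:

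1. **Power.** In a logistic-type model, leaving out a prognostic covariate makes the treatment test less powerful.
2. **Chance imbalance.** With only 30 control patients the arms can differ noticeably in baseline severity, and the site-only estimate absorbs that difference. If adjustment is added only after an imbalance is seen, the adjusted result is post hoc and open to challenge.

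**Working it through.** **1. The plan's own figure.** Section 13.2 states 80% power for d = 0.44 on the primary group-by-time effect (30 vs 60, 40% dropout, correlation 0.5, two-sided 0.05). It gives neither the number of occasions nor the retention pattern. With the 14 occasions of 13.3.1 and the 40% lost evenly over 14 intervals, generalised least squares gives a minimum detectable d of 0.447.

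- Standard error = 0.447 / (1.960 + 0.842) = 0.1595
- Power = Φ(0.44/0.1595 − 1.960) = Φ(0.80) = 79%

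Other reasonable retention patterns and numbers of occasions, or a common intercept, give 77% to 83%. The stated figure is reproduced, but it says nothing about the ordinal outcome.

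**2. Power of the ordinal test without a baseline covariate.** The Whitehead approximation is power = Φ(|log OR|·√V − 1.96), with V = n₁n₂N / [3(N+1)²] × (1 − Σp̄³), where p̄ are the pooled category proportions.

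- Assumed control levels are 0.40/0.20/0.40, from the plan's 40% dropout and the 41–46% transition rate cited in 7.1.3. The split of completers is an assumption.
- At OR 3 the treated levels are 0.182/0.151/0.667, so p̄ = 0.255/0.168/0.578 and 1 − Σp̄³ = 0.786.
- V = 60·30·90/(3·91²) × 0.786 = 6.52 × 0.786 = 5.13
- Power = Φ(1.099 × 2.264 − 1.96) = Φ(0.53) = 70%

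Across the control levels tried, power is about 36% at OR 2, 56% at OR 2.5 and 70–72% at OR 3. An OR of about 3.4 to 3.5 is needed for 80%. Power for this outcome is scarce.

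**3. Gain from one baseline covariate.** The documents do not give its prognostic strength, so a range is shown. Set-up: 60 vs 30; control levels 0.59/0.15/0.26 (41% completion on lofexidine, section 7.1.5; split assumed); conditional treatment OR 3; 1,500 simulated trials per setting; likelihood-ratio test.

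| Assumed OR per SD of baseline severity | Unadjusted | Adjusted | Gain |
|---|---|---|---|
| 1.5 | 73% | 73% | 0 points |
| 2 | 66% | 70% | 4 points |
| 3 | 56% | 68% | 12 points |

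A separate simulation included the site terms and held the marginal OR at 3, with control levels 0.40/0.20/0.40. With severity at OR 2 per SD, power rose from 72.1% to 75.9%, about 4 points again. The adjusted model there also carried a second covariate with no effect.

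When the covariates had no prognostic value, adjustment cost nothing visible: 71.2% vs 71.3%, and 73.5% vs 73.4% with control levels 0.59/0.11/0.30.

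**4. Chance imbalance.**

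- SD of the baseline difference = √(1/60 + 1/30) = 0.224 SD units
- P(|difference| > 0.3 SD) = 2[1 − Φ(0.3/0.224)] = 2[1 − Φ(1.34)] = 18%
- 95% of trials lie within ±1.96 × 0.224 = ±0.44 SD

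With severity at OR 2 per SD, the site-only log OR moved by 0.56 to 0.71 per SD of imbalance across the simulated settings. A 0.3 SD difference therefore shifts the OR by a factor of e^(0.3×0.56) = 1.18 to e^(0.3×0.71) = 1.24. A 0.44 SD difference shifts it by 1.28 to 1.37. After adjustment the slope was between −0.07 and 0.10, close to zero.

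**5. Validity.** Under no treatment effect the site-only test rejected in 5.1% to 6.6% of simulated trials. The model with two covariates rejected in 4.9% to 7.5% (Monte Carlo standard error about 0.6 points).

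**The case against.** **The analysis is not wrong.** This stands. A reader might infer that the site-only odds ratio is biased or its test invalid, but neither follows. Type I error is near nominal, and randomisation means that chance imbalance is not systematic and is already reflected in the standard error. The pull of the odds ratio toward 1 is non-collapsibility: in the simulation, a marginal OR of 3.0 corresponds to a conditional OR of 3.31 when severity has OR 2 per SD. These are two different estimands.

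**Day 1 fentanyl.** A reader might also infer that Day 1 urine fentanyl belongs in the model because XR-NTX is offered to patients "if they provide a urine sample that is negative for opioids, buprenorphine, and fentanyl". The documents do not support that. The condition concerns the Day 8 urine, and nothing ties Day 1 status to the outcome. Section 10.11 schedules the test as "Done at Screen, Day 1, Day 8/9, Day 10, and Day 15" and gives no timing relative to the first dose. If nearly all patients are positive it would also add almost nothing (70.8% vs 70.7% at an assumed 95% prevalence and OR 2).

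**The SOWS link is partly inference.** Sections 13.3.1 and 10.13.3 speak of withdrawal in general or during the study, not of the pre-dose score. That is fair, and it is why the prognostic strength is left as a range starting at no gain. The pre-dose score is also cut off below at 4, may have several values, and may partly reflect how long staff waited. A screening value can be up to 30 days old. These points govern how the covariate is defined; they do not remove the case for it.

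**The gain may be small, on a secondary outcome of a Phase 2 trial.** This also stands. The largest gain needs an OR of 3 per SD from a truncated score. Section 7.1.6 leaves well-powered testing to a later trial.

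Sex, which stratifies the randomisation but is absent from this model, is a separate matter.

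**Conclusion.** The point holds as an efficiency improvement. The planned test may stand as valid, but the model ignores a baseline measure already in hand that the protocol's own reasoning makes plausibly prognostic. At a treatment OR of about 3 the power given up is about 0 to 12 points. A gain of about 4 points goes with an OR of 2 per SD.

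These figures rest on assumed control proportions, an assumed treatment effect and an assumed prognostic strength, none of which the documents give for this outcome. The 18% chance of an imbalance above 0.3 SD needs only the 60:30 allocation. How far that moves the odds ratio again depends on the assumed strength.

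**What to change.** In 13.3.2, add the SOWS-Gossop total as one linear covariate next to site and group, and state:

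- **Definition:** the last total recorded before the first dose of study medication. This settles which value counts when the scale is repeated.
- **Missing values:** a simple rule set in advance, for example mean imputation blind to group, rather than an older screening score.
- **Estimand:** the odds ratio is conditional on baseline severity as well as site.
- **Sensitivity analysis:** the site-and-group model as now written.

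Day 1 fentanyl need not be a required covariate. With 90 patients the covariates should be few, since the two-covariate test ran slightly above 5% in some null settings.

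The cost is a few lines in the plan, one model term and a conditional odds ratio, with no new data collection. The change should be made before unblinding so that the adjustment is not post hoc.

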13.4 SAFETY OUTCOMES

- 13.4.1 Suicidality. We will compare the groups on presence of active suicidal ideation on the basis of the C-SSRS, which will be administered daily. We define Active Suicidal Ideation to be an endorsement of either Question 4 (active ideation without plan) or 5 (active ideation with plan). If there is sufficient variability in these repeated binary outcomes, we will compare the groups using a mixed effects logistic regression model, similar to the linear mixed effects models described above for the primary outcome; if variability is too low, we will use a (non-mixed-effects) logistic regression model to compare the groups on proportion of participants reporting active ideation at any time in the period
- **13.4.2 Sedation.** The POSS will be administered four times a day on dose days, yielding a set of repeated measures on the POSS score for each participant. We will compare the groups on this score, using linear mixed effects models similar to those described above for the primary outcome.
- **13.4.3** Elevated Creatine Kinase. On day 8 of detoxification, participants will be classified as having elevated creatine kinase if their level is more than three times their screening level. We will compare groups on this response using a logistic regression model with site and group as explanatory variables.
- **13.4.4_Edema**. We will compare groups on the proportion of participants whose study medications were discontinued due to peripheral edema, using a logistic regression model with site and group as the explanatory variables.

